#### **9.4.2 Radiographic Disease Assessment According to Prostate Cancer Clinical Trials Working Group (PCWG2) and Modified Response Criteria in Solid Tumors (RECIST Version 1.1)**

Radiographic Disease Assessment will be performed using the PCWG2 guidelines. The PCWG2 recommends that for soft tissue lesions RECIST 1.1 assessment be applied and that results be compiled separately from the overall disease assessment, which includes both bone scan and RECIST 1.1 results.

Under RECIST 1.1, radionuclide bone scan lesions are considered not measurable, and hence nontarget. Under RECIST, bone scan progression occurs when the changes are "unequivocal." Under PCWG2, however, radionuclide bone scan results are treated semi-quantitatively and occurrence of new lesions may define progression as outlined further below. For this protocol, soft tissue and bone scan disease are evaluated separately, and the results of each are then considered in an overall radiographic disease assessment.

#### **9.4.3 Recording Baseline Assessments**

All sites of disease, target and nontarget lesions must be assessed at baseline. Patients with visceral metastases will be excluded from the protocol. Objective disease status is to be recorded at each evaluation using the response categories and definitions provided in this section.

#### **9.4.4 Soft Tissue Lesion Assessment**

##### **Selection of Target and Nontarget Lesions**

##### **Selection of a Lymph Node as a Target Lesion**

Only lymph nodes with a longest diameter  $\geq 2$  cm and a minimum short axis diameter  $\geq 1.5$  cm by CT scan will be considered as target lesions at baseline. All other lesions may be considered as nontarget, and are to be identified but not specifically measured at baseline, with the exception of bone scan metastases, which are identified and enumerated.

## 9.4.5 Response Definitions for RECIST-Evaluable Soft Tissue Lesions

### 9.4.5.1 Definition of Complete Response (CR)

Disappearance of all target lesions. Any pathological lymph nodes (whether target or nontarget) must have reduction in short axis to < 10 mm.

### 9.4.5.2 Definition of Partial Response (PR)

At least a 30% decrease in the sum of diameters of target lesions, taking as reference the baseline sum of longest diameters of non-lymph node lesions and of the short diameter(s) or short axis (SA) of lymph nodes.

### 9.4.5.3 Definition of Stable Disease (SD)

Neither sufficient shrinkage to qualify for PR nor sufficient increase to qualify for PD, taking as reference the smallest sum of diameters while on study.

### 9.4.5.4 Definition of Soft Tissue Progression

At least a 20% increase in the sum of longest diameters of target lesions, taking as reference the smallest sum on study (this includes the baseline sum if that is the smallest on study). In addition to the relative increase of 20%, the sum must also demonstrate an absolute increase of at least 5 mm.

NOTE: The appearance of 1 or more new measurable lesions is also considered progression.

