### 5.1 Inclusion Criteria

**Yes/No (Response of "no" = patient ineligible)**

- 5.1.1** \_\_\_\_\_ Histologically documented adenocarcinoma of the prostate.
- 5.1.2** \_\_\_\_\_ Men at least 18 years of age and life expectancy of  $\geq$  6 months.
- 5.1.3** \_\_\_\_\_ ECOG performance status  $\leq$  2.
- 5.1.4** \_\_\_\_\_ Metastatic disease as evidenced by both lymphadenopathy and bony metastases or just bony metastases on baseline bone scan and / or computed tomography (CT) scan or MRI of the abdomen and pelvis within 28 days of registration. Chest imaging is only required if clinically indicated or if there is known disease in the chest.
- 5.1.5** \_\_\_\_\_ Castration resistant prostatic adenocarcinoma. Subjects must have castrate levels of serum testosterone ( $< 50$  ng/dL) achieved by orchiectomy or LHRH agonist or antagonist therapy.
- 5.1.6** \_\_\_\_\_ Previously received docetaxel or are not healthy enough per clinical judgment or declined to receive it.
- 5.1.7** \_\_\_\_\_ Evidence of disease progression on or after the most recent systemic treatment defined by one of the following criteria:

PSA: Increasing serum PSA levels as defined by the PCWG2, determined by 2 consecutive measurements (compared to a baseline or nadir value). If the third measurement is below the second, then a fourth measurement must be greater than the second. The confirming third or fourth measurement must be  $\geq$  2 ng/mL. PSA progression must have occurred within 15 months of registration (with at least 7 days between each PSA measurement). Additionally, the PSA progression as described above should have occurred during or after the most recent systemic treatment for prostate cancer.

Measurable disease:  $\geq$  20% increase in the sum of the short axis diameter of all measurable lymph nodes or the development of

any new measurable lymphadenopathy by RECIST 1.1 and PCWG2 criteria.

Non-measurable disease:

*Lymph node disease:* Appearance of 1 or more new lymphadenopathy, and / or unequivocal worsening of non-measurable disease when compared to imaging studies acquired during castration therapy or against the pre-castration studies if there was no response.

*Bone disease:* Appearance of 2 or more new areas of abnormal uptake on bone scan when compared to imaging studies acquired during castration therapy or against the pre-castration studies if there was no response. Increased uptake of pre-existing lesions on bone scan does not constitute progression.

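### On-study soft-tissue progression (9.4.5.4) is measured on longest diameters, while response and entry progression use the nodal short axis, so progression, stable disease and response are read from different sums

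*Combined protocol and SAP*

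**What the plan says.** - **Progression on study (9.4.5.4):** "At least a 20% increase in the sum of longest diameters of target lesions, taking as reference the smallest sum on study". In addition, "the sum must also demonstrate an absolute increase of at least 5 mm". Nodes are not treated separately.
- **Target lesions (9.4.4):** "Only lymph nodes with a longest diameter" of at least 2 cm and a short axis of at least 1.5 cm "by CT scan will be considered as target lesions at baseline. All other lesions may be considered as nontarget". Section 9.4.3 adds: "Patients with visceral metastases will be excluded from the protocol".
- **Partial response (9.4.5.2):** a fall of at least 30% from "the baseline sum of longest diameters of non-lymph node lesions and of the short diameter(s) or short axis (SA) of lymph nodes".
- **Complete response (9.4.5.1):** pathological nodes must shrink below 10 mm in short axis.
- **Stable disease (9.4.5.3):** whatever lies between partial response and progression, with the smallest sum of diameters as reference. This presupposes a single sum.
- **Progression at entry (5.1.7, measurable disease):** at least a 20% "increase in the sum of the short axis diameter of all measurable lymph nodes".

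**The concern.** Every rule on nodal size change uses the short axis except the on-study progression rule, which uses the longest diameter. Response and progression are then not two ends of one scale. The reference sum for progression is a different quantity from the baseline sum for partial response, and stable disease has no single sum on which to rest. Table 8 has no row for a target set that meets both partial response and progression.

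The call has consequences. Under Table 9, soft-tissue progression makes the overall assessment progression even when the bone scan is stable. Progression during treatment is a reason for withdrawal (6.6) and a radiological progression event, and it fixes the final N-telopeptide time point when it precedes end of treatment (10.1.1). Two readers, one following 9.4.5.4 literally and one carrying over the short axis from 9.4.5.2, could date progression differently in the same patient.

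**Working it through.** The plan gives no figure to reproduce here. The check applies its own thresholds to single target nodes that satisfy 9.4.4 (longest diameter at least 20 mm, short axis at least 15 mm) and 5.2.11 (short axis not above 30 mm). In each example the baseline is also the smallest sum on study.

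Rules applied (LD = longest diameter, SA = short axis):
- Progression as written: LD up at least 20% and at least 5 mm.
- Progression on the response axis: SA up at least 20% and at least 5 mm.
- Partial response: SA down at least 30%.

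| Node, LD x SA (mm) | LD change | SA change | As written | On short axis |
|---|---|---|---|---|
| 30 x 15 to 31 x 20 | 31/30 = 1.03: +3%, +1 mm | 20/15 = 1.33: +33%, +5 mm | no progression | progression |
| 25 x 20 to 31 x 20 | 31/25 = 1.24: +24%, +6 mm | 20/20 = 1.00: 0% | progression | no progression |
| 20 x 16 to 25 x 11 | 25/20 = 1.25: +25%, +5 mm | 11/16 = 0.69: -31% | progression and partial response | partial response |

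**How unusual is the third row?** To meet both rules, LD must grow by a factor of at least 1.2 while SA shrinks to at most 0.7 of baseline. The LD/SA ratio must therefore rise by at least 1.2/0.7 = 1.71. In the example it goes from 20/16 = 1.25 to 25/11 = 2.27. That is a marked change of shape. The first two rows need nothing comparable.

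**Which scans can move the primary sample?** Study Calendar note 6 schedules two post-baseline scans in the treatment period: end of cycle 3 (3 x 4 = week 12) and the end-of-treatment visit, which note 10 places 4 weeks after C6D1 (5 x 4 + 4 = week 24).
- At the end-of-treatment scan the N-telopeptide sample is due anyway, so a discordant call there does not materially move it.
- At the end-of-cycle-3 scan a discordant call could move the final sample from about week 24 to about week 12, or fail to. New bone lesions at that scan need later confirmation (9.4.6.2); 9.4.5.4 asks for none in soft tissue.
- Unscheduled scans for suspected progression (9.4.1) are the only other route.

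**After treatment** progression is left to the treating clinician's judgement (6.6, 9.4.1), so the 9.4.5.4 threshold does not formally govern later dates.

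**The case against.** **Section 9.4.2 refers soft tissue to RECIST 1.1, and a harmonising reading exists.** The reference in 9.4.5.4 includes the baseline sum, the only baseline sum defined is the one in 9.4.5.2, and 9.4.5.3 speaks of one sum. This makes loose drafting more likely than a deliberate second measure, and a reader should not infer the latter. It does not cure the text: 9.4.5.4 states an explicit rule, and nothing says that the general reference overrides it.

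**Nodes may not be the only target lesions.** Section 9.4.2's successor rules leave some room: 9.4.5.2 mentions non-nodal lesions, the sentence in 9.4.4 can be read as saying which nodes qualify, and excluding visceral metastases does not by itself exclude all other soft tissue. So the statement that only nodes can be targets is slightly firmer than the text. The inconsistency for nodes stands on either reading.

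**Simultaneous response and progression is contrived.** Largely accepted. A reader might take that overlap as the main problem, but it needs an unusual shape change. The likelier consequence is a progression call or date that depends on the axis used.

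**The effect on endpoints is small.** This stands in good part. A reader might infer that the primary endpoint is broadly compromised, or that rPFS is biased throughout follow-up. The scan schedule and the clinician-judged progression after treatment do not support either inference. rPFS is listed among exploratory variables and analyses other than the primary ones are descriptive (10.2), so no planned test rests on it.

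**Conclusion.** Wrong as written, with limited reach. Section 9.4.5.4 cannot be applied consistently with 5.1.7, 9.4.5.1, 9.4.5.2 and 9.4.5.3 in a patient whose target lesions are nodes, and the examples show the classification changing in both directions.

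The effect is confined to patients with qualifying target nodes. Bone-only disease is eligible (5.1.4), and the documents do not give the share with target nodes, so the total effect cannot be quantified. Within that group it is confined to on-treatment scans. It bears directly on radiological progression and rPFS. It bears on the primary endpoint only through a discordant call at the end-of-cycle-3 scan or at an unscheduled scan, in a patient who has not progressed by another route. For scale, one such patient would be 1/12 = 8.3% of the planned evaluable control arm or 1/27 = 3.7% of the randomized combination arm. These are illustrations, not expected counts.

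The arithmetic assumes a single target node whose baseline is the smallest sum on study.

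**What to change.** Reconcile 9.4.5.4 with 5.1.7, 9.4.5.1, 9.4.5.2 and 9.4.5.3 so that one sum is used throughout. For example, in 9.4.5.4 replace the reference to longest diameters by: *sum of diameters of target lesions (short axis for lymph nodes)*. The 20% and 5 mm limits stay as they are. The wording also works if a non-nodal target lesion is ever recorded.

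Against the same reference, one sum cannot fall 30% and rise 20% at once, so the overlap in the third example disappears. A sum can still lie 30% below baseline and 20% above a lower nadir, because the two rules use different references. One added sentence should say which category is recorded then.

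The cost is a short amendment. The short axis is already needed for target selection and response, so no new measurement is required. Any on-treatment nodal assessments already made under the present text should be re-read on the reconciled sum.

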### 9.4.5.5 Assessment of Soft Tissue Time Point Response

The following table summarizes the RECIST 1.1 response status calculation at each time point for patients who have measurable soft tissue disease at baseline. Note that this assessment does not include bone scan assessment and is not the overall assessment of radiographic disease status.

**Table 8: Time Point Response: Patients with Target (± Nontarget) Disease**

Target lesions	Nontarget lesions	New lesions	Overall response
CR	CR	No	CR
CR	Non-CR/non-PD	No	PR
CR	Not evaluated	No	PR
PR	Non-PD or not all evaluated	No	PR

SD	Non-PD or not all evaluated	No	SD
Not all evaluated	Non-PD	No	NE
PD	Any	Yes or No	PD
Any	PD	Yes or No	PD
Any	Any	Yes	PD

Source: Eisenhauer EA, Therasse P, Bogaerts J, Schwartz LH, Sargent D, Ford R, et al. New response evaluation criteria in solid tumours: revised RECIST guideline (version 1.1). Eur J Cancer 2009;45(2):228-47.

Abbreviations: CR = complete response; PR = partial response; SD = stable disease; PD = progressive disease; NE = not evaluable.

## 9.4.6 Radionuclide Bone Scan Assessment

### 9.4.6.1 Assessment

Bone scan lesions should be enumerated at baseline. Questionable lesions, eg, sites of previous fracture, may require confirmation by CT or MRI.

### 9.4.6.2 Post baseline Assessments and Definition of Progression of Bone Metastatic Disease Based on Radionuclide Bone Scan

Bone scan lesions should be assessed and enumerated at each follow-up assessment.

Progression on bone scan is defined as 2 or more new lesions on radionuclide bone scans. Should 2 or more new bone lesions be evident at the first assessment on treatment (end of cycle 3), 2 or more additional new lesions must be evident on a confirmatory assessment at least 6 weeks later (and no sooner than end of cycle 6). This confirmation is not required when 2 or more new lesions (compared to baseline or to the end of cycle 3 assessment) first appear after the first follow-up assessment, ie, at end of cycle 6 or thereafter.

Should new bone lesions be documented at end of cycle 3 but not confirmed at end of cycle 6, then end of cycle 3 scan becomes the new baseline and 2 or more new lesions at subsequent assessments relative to end of cycle 3 defines bone scan progression.

Stable disease (SD) on bone scan stable disease is defined as the absence of progression. Bone scan lesions are considered non-evaluable under RECIST, and thus there can be no partial response. Complete response is very rare. Thus, almost all bone scans will be rated as NE (no lesions present), SD, or PD.

#### 9.4.7 Overall Response Assessment

The following table summarizes the overall response status calculation at each time point for patients who have either RECIST 1.1 evaluable soft tissue lesions and / or radionuclide bone scan lesions. Note that CR can only occur if there are RECIST 1.1-evaluable lesions and no bone lesions based on radionuclide bone scan. PR can occur if patients have CR or PR based on soft tissue evaluation and bone scan lesions that are stable.

**Table 9: Overall Assessment Time Point Response**

PCWG2 Target/Nontarget soft tissue/RECIST 1.1	Bone Scan (PCWG2)	Overall
CR	No Metastases	CR
CR,PR	SD	PR
SD	SD	SD
PD	SD	PD
SD	PD	PD

#### 9.4.8 Progression Free Survival

Progression Free Survival by prostate-specific antigen (PSA) will be assessed for each patient on this study. Time to PSA progression is the time from the date of the first study drug administration to the first date that PSA progression is observed, according to the definitions below. Patients will have their PSA levels measured monthly while on study treatment. After the end of treatment visits, PSA assessments should be performed every 4-6 weeks visit until disease progression, or the start of another treatment.

##### Definition of PSA response:

- $\geq 30\%$  reduction of the blood level, compared to the baseline value.
- $\geq 50\%$  reduction of the blood level, compared to the baseline value.
- $\geq 90\%$  reduction of the blood level, compared to the baseline value.
- Confirmed PSA response:  $\geq 50\%$  reduction of the blood level, compared to the baseline value, confirmed by a second PSA value approximately 4 or more weeks later.

##### Definition of PSA Progression:

- In patients with no PSA decline from baseline;  $\geq 25\%$  increase from baseline value and an increase in absolute value of  $\geq 2$  ng/mL, at least 12 weeks from baseline.
- In patients with initial PSA decline from baseline; the PSA increase that is  $\geq 25\%$  and at least 2 ng/mL above the nadir value, which is confirmed by a second value obtained three or more weeks later.

##### Changes and time to progression in total-ALP:

- Total-ALP response and progression; defined as for PSA above.

## 10 STATISTICAL METHODS AND SAMPLE SIZE DETERMINATION

### General considerations

Statistical analyses will be performed using Statistical Analysis Software®; the version to be used will be specified in the SAP.

### Determination of sample size of the randomized cohort

Serum N-telopeptides levels are inversely associated with overall survival, based on data from the SWOG 0421 trial. The primary endpoint for statistical analysis for this study will a comparison of the change in N-telopeptides from baseline to EOT or at disease progression (whichever comes earlier) between the randomization groups. The change in log 2 N-telopeptides will be compared to the change in a control group treated with enzalutamide alone using an ANCOVA model with the final value as response, treatment group as predictor and initial log 2 N-telopeptides as an adjustment variable. Based on the data from the SWOG 0421 study, the estimated baseline mean and standard deviation of log2 N-telopeptides are 3.95 nM and 1.14 nM respectively. We further assume the Pearson correlation of baseline and follow up N-telopeptides is 0.50. With these assumptions, and with 27 evaluable patients in the radium-223 + enzalutamide arm and 12 evaluable patients in the enzalutamide only arm there will be 85% power to detect a difference of 1.14 in the change in log 2 N-telopeptides between treatment arms using a two-sample t-test at the two-sided 0.05 significance level.

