## **4 STUDY DESIGN**

### **4.1 Description**

This is a phase 2, open label, randomized, two arm study in men with progressive metastatic CRPC who have previously received docetaxel or are ineligible for docetaxel and who are candidates for treatment with enzalutamide alone or enzalutamide in combination with radium-223. The study will assess the difference between the combinatorial treatment and enzalutamide alone on the bone metabolism markers, including the decrease in N-telopeptide levels (i.e. decrease of 0.603 in log2 N-telopeptides) from baseline to after 6 months of protocol treatment, as well as assess the safety and feasibility of the combinatorial regimen.

The study has an initial non-randomized single arm portion (enzalutamide + radium-223, n = 8 patients) followed by a randomized (2:1) portion comparing enzalutamide + radium-223 versus enzalutamide alone (n = 39 patients) as shown in Figure 1 below.

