#### **10.1.1 Primary Bone Marker Analysis**

Concomitant treatment with radium-223 (a bone targeting agent) and enzalutamide (a tumoricidal agent) is expected to decrease the level of N-telopeptides. As mentioned in the Background Section, serum N-telopeptides levels are inversely associated with overall survival, based on data from the SWOG 0421 trial. The primary endpoint for statistical analysis for this study will be the change in log 2 N-telopeptides from baseline to EOT or at disease progression (whichever comes earlier) between the randomization groups. If a bone marker test is missed at a given time point, every effort will be made to obtain the bone marker levels as early as possible. If two subsequent bone marker tests are missed, the patient will be excluded from the analysis. Equality of the change in log2 N-telopeptides between the treatment arms will be tested using an ANCOVA model with treatment group as the primary predictor and initial log 2 N-telopeptides as adjustment variable.

As a sensitivity analysis an F-test for equality of variance of final log2 N telopeptides will be performed. If the null hypothesis is rejected at the 0.1 significance level an additional ANCOVA model allowing for unequal variances will be fit.

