#### **10.1.2 Additional Analyses of the Primary Endpoint**

Separate analyses in the combined population will be performed in subjects treated with enzalutamide + radium-223 and subjects treated with enzalutamide alone. If a bone marker test is missed at a given time point, every effort will be made to obtain the bone marker levels as early as possible. If two subsequent bone marker tests are missed, patient will excluded from the analysis.

Based on the data from the SWOG 0421 study, the estimated baseline mean and standard deviation of log2 N-telopeptides are 3.95 nM and 1.14 nM respectively. We further assume the Pearson correlation of baseline and follow up N-telopeptides is 0.50. With 35 evaluable subjects there will be 80% power to detect a change of 0.556 in log2 N-telopeptides using a paired t-test. Extrapolating from SWOG0421, a decrease of 0.556 in log2 N-telopeptide concentration would translate into an approximate 20% increase in median overall survival.

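### The 85% power stated for the primary comparison fits neither the t-test it names (80%) nor the planned ANCOVA (about 89%), and the 0.603 decrease in Section 4.1 has no counterpart in Section 10

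*Combined protocol and SAP*

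**What the plan says.** Section 10, under the heading on sample size of the randomized cohort, plans an "ANCOVA model with the final value as response, treatment group as predictor and initial log 2 N-telopeptides as an adjustment variable". Section 10.1.1 confirms the same kind of model for the primary test: "ANCOVA model with treatment group as the primary predictor and initial log 2 N-telopeptides as adjustment variable".

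The power in that sample size paragraph is given for a different test, a two-sample t-test with a two-sided level of 0.05. Its inputs are that "the estimated baseline mean and standard deviation of log2 N-telopeptides are 3.95 nM and 1.14 nM respectively" and "We further assume the Pearson correlation of baseline and follow up N-telopeptides is 0.50", with 27 evaluable combination patients and 12 evaluable controls. The claim is that "there will be 85% power to detect a difference of 1.14 in the change in log 2 N-telopeptides between treatment arms".

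Section 10.1.2 repeats the SD and correlation for a within-arm analysis: "With 35 evaluable subjects there will be 80% power to detect a change of 0.556 in log2 N-telopeptides using a paired t-test".

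Section 4.1, in a sentence about the difference between the combination and enzalutamide alone, gives a third effect size: "decrease of 0.603 in log2 N-telopeptides) from baseline to after 6 months of protocol treatment".

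**The concern.** The power statement should follow from the inputs printed beside it, and it should describe the analysis that will be run. Here it appears to do neither. It names a t-test on change scores although the primary analysis is an ANCOVA, and the figure looks too high for the t-test and too low for the ANCOVA.

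This paragraph is the only quantitative support in the plan for a 12-patient control arm. The 35 combination patients have separate justification in Sections 10.1.2 (paired test) and 10.1.3 (safety), but the controls do not. A reader who tries to verify the size of the randomized comparison cannot reproduce it. If that reader starts from Section 4.1, the effect named there appears nowhere in the sample size section.

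**Working it through.** **Inputs from the plan.** Baseline SD 1.14; baseline to follow-up correlation r = 0.50; n = 27 and 12; difference 1.14; two-sided 0.05 (all from the sample size paragraph of Section 10). Paired test: change 0.556, n = 35, 80% (Section 10.1.2). Decrease 0.603 (Section 4.1).

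**Assumption.** The follow-up SD is not stated. I take it as 1.14. Then SD of change = 1.14 × √(2 × (1 − 0.50)) = 1.14. All powers below use the noncentral t distribution.

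**Step 1: does the assumption reproduce a figure in the plan?** Paired test: noncentrality = (0.556 / 1.14) × √35 = 2.885, df 34, power 80.04%. Section 10.1.2 says 80%, so equal SDs match the plan's own calculation.

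**Step 2: the named two-sample t-test.** Noncentrality = (1.14 / 1.14) × √(27 × 12 / 39) = 2.882, df 37. Power is **80.1%**, against the stated 85%. A normal approximation gives 82.2%, so approximation does not close the gap.

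**Step 3: the planned ANCOVA.** Residual SD = 1.14 × √(1 − 0.50²) = 0.987, df 36. Noncentrality = (1.14 / 0.987) × 2.882 = 3.328, giving 89.9% if the cost of estimating the covariate effect is ignored. Allowing for chance baseline imbalance gives **89.1%**; simulation of the ANCOVA test gives 89.2%.

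**Step 4: can one SD of change satisfy both sections?** The t-test reaches 85% at an SD of change of 1.068. At r = 0.50 that means a follow-up SD of about 0.98; with both SDs at 1.14 it means r of about 0.56. At 1.068 the paired test has 84.9% power, not the 80% stated. The two statements cannot both be right on shared inputs.

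**Step 5: detectable differences (27 versus 12, equal SDs).**

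| Test | 80% power | 85% power |
|---|---|---|
| Two-sample t-test on change | 1.14 | 1.22 |
| ANCOVA | 1.00 | 1.07 |

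**Step 6: sensitivity of power for a difference of 1.14.** The follow-up SDs of 0.98 and 1.30 and the correlations of 0.40 and 0.60 are illustrative values, not figures from the plan.

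| Follow-up SD | r | t-test | ANCOVA |
|---|---|---|---|
| 1.14 | 0.50 | 80% | 89% |
| 0.98 | 0.50 | 85% | 96% |
| 1.30 | 0.50 | 74% | 80% |
| 1.14 | 0.40 | 73% | 85% |
| 1.14 | 0.60 | 88% | 93% |

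**Step 7: the 0.603 in Section 4.1.** Read as a within-arm paired change with SD 1.14, power is 75% with n = 27, 80.0% with n = 30 and 86% with n = 35. The plan has no group of 30. Only if 0.603 were read as the between-arm difference would power be 32% (t-test) or 39% (ANCOVA). Section 10 contains 1.14 and 0.556 but not 0.603.

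**The case against.** Four points can be made for the plan.

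- **The follow-up SD is unstated, so 85% might be right for some value.** This is true: about 0.98 gives 85% by t-test, and about 1.21 gives 85% by ANCOVA. Neither value is in the plan, and each breaks Section 10.1.2, where the paired power would become about 85% or about 77% instead of 80%. One could suppose a different SD of change in the two calculations, but both sections cite the same SD and correlation. What stands is that the 80% and 89% depend on equal SDs and should be quoted with that condition.
- **Sizing an ANCOVA by a t-test on change is an accepted, conservative shortcut.** That is fair, and the mismatch of tests alone would be a minor matter. It does not rescue the number, because the shortcut gives 80%.
- **Nothing turns on it, because the planned test exceeds 85%.** This stands as far as consequence goes: under equal SDs the stated figure understates the power of the primary analysis. The statement itself remains wrong.
- **The 0.603 is worded as a change from baseline, and Section 10 gives the between-arm 1.14 clearly.** This largely stands, so the low between-arm powers are conditional on a reading that the words do not favor. But the figure sits in a sentence about the difference between arms and agrees with neither effect size in Section 10. It may be left over from a calculation with 30 patients; the documents do not confirm that.

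One further explanation was tried: counting all 35 combination patients against 12 controls. That gives 83.3% (84.8% by normal approximation), but it contradicts the stated 27 and would include the 8 non-randomized patients, whom Section 4.1 excludes from the primary analysis.

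**Conclusion.** The point holds. With the plan's inputs and a follow-up SD equal to the baseline SD, power for a between-arm difference of 1.14 is 80.1% by the named t-test, 4.9 points below the stated 85%, and about 89% by the planned ANCOVA, about 4 points above it. The equal-SD assumption is not stated, but it is the one that reproduces Section 10.1.2. The 0.603 in Section 4.1 is unsupported by Section 10.

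This is an error of statement and justification. It does not show the trial to be underpowered: the ANCOVA keeps about 80% power even if the follow-up SD is 1.30 at r = 0.50. It should be corrected because it is the only stated basis for the size of the control arm.

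**What to change.** **Section 10, sample size paragraph.** The trial statistician should confirm the follow-up SD and give the power for the planned test. If equal SDs were intended, for example: *ANCOVA adjusting for baseline log2 NTx, follow-up SD assumed 1.14, correlation 0.50 (residual SD 0.987), 27 versus 12, two-sided 0.05: about 89% power for a between-arm difference of 1.14 (80% for about 1.0); about 96% if the follow-up SD is 0.98 and 80% if it is 1.30.* If the t-test basis is kept, replace 85% with 80%.

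**Section 4.1.** Reword the sentence instead of swapping the number, because 0.603 is a change from baseline and 1.14 is a difference between arms. For example: *including the difference between arms in the change in log2 N-telopeptides from baseline to EOT or disease progression, whichever comes earlier (difference used for sample size: 1.14).* Delete 0.603, or identify it as a within-arm change and reconcile it with the 0.556 in Section 10.1.2.

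**Cost.** Wording in two sections. Patient numbers, primary test and visit schedule are unchanged.
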